5.1. Rationale for Amendment (a)

This protocol was amended so that the initial dose of abemaciclib when administered in combination with fulvestrant could be lowered from 200 mg every 12 hours (Q12H) to 150 mg Q12H.

Additionally, existing patients who have already started on 200 mg of blinded study drug will be dose reduced to 150 mg Q12H.

Further modifications were performed for clarity: 1) blinded study drug in relevant places defined; 2) supportive management for diarrhea modified. Minor typographical and formatting edits were made throughout the document for clarity and consistency.

5.1.1. Dose Rationale

The rationale for reducing and selecting the starting dose was based on the preliminary blinded safety review of Study JPBL and updated safety and pharmacokinetic/pharmacodynamic (PK/PD) data from patients treated with endocrine therapies in combination with abemaciclib in advanced or metastatic breast cancer enrolled in Studies JPBA and JPBH.

Pharmacokinetic data obtained in Study JPBA for abemaciclib from a total of 124 patients dosed repeatedly with abemaciclib at 150 and 200 mg Q12H indicate that the range of steady-state exposures achieved with 150 mg Q12H is comparable to 200 mg Q12H. In addition, in Study JPBA the steady-state exposures achieved with a 50-mg unit dose, which is the lowest possible allowed dose in Study JPBL in the case of dose reduction when needed for AEs, are within the low end of the range of exposures achieved by the 150- and 200-mg dose levels. Skin biopsies collected in Study JPBA predose and 4 hours postdose on Cycle 1 Day 15 show a decrease in the pRb and topoiI α expression with increasing plasma concentration. Abemaciclib effectively inhibits CDK4/6, which results in cell cycle inhibition upstream of the G1 restriction point at both doses of 150 and 200 mg.

Tumor responses were observed in patients receiving both 150 mg and 200 mg abemaciclib monotherapy. As of 29 August 2014, findings in the 47 patients with advanced or metastatic breast cancer who have been enrolled in Part D of Study JPBA resulted in 12 confirmed PRs (including 8 responses at 150 mg Q12H and 4 responses at 200 mg Q12H) among the 36 patients in Part D with HR+ mBC, based on investigators' assessment of response using RECIST v1.1. The ORR for the 36 patients in Part D with HR+ mBC was 33.3%, the DCR was 80.6%, the CBR was 61.1%, and median PFS was 8.8 months.

In a subsequent cohort of 19 patients with HR+, advanced or metastatic breast cancer enrolled in Part G of Study JPBA and treated with fulvestrant plus 200 mg abemaciclib Q12H, 17 patients

with abemaciclib dose reductions were observed. In addition, 4 confirmed PRs were observed for an ORR was 21.1% (36.4% in the 11 patients with measurable disease), the DCR was 78.9%, the CBR was 63.2%, and the median PFS was 10.2 months.

Preliminary safety data from Study JPBH demonstrate that the AE profile of abemaciclib administered in combination with nonsteroidal aromatase inhibitors (NSAIs) is consistent with abemaciclib monotherapy, as the most common TEAEs possibly related to study drug were diarrhea, nausea, fatigue, and neutrophil count decreased. However, at the 200-mg dose, the incidence of treatment-emergent Grade 3 diarrhea was found to be greater when abemaciclib was administered in combination with an NSAID from a review of the preliminary safety data in Study JPBH, compared to abemaciclib administered alone in Part D of Study JPBA. Nevertheless, when the abemaciclib dose was reduced from 200 mg to 150 mg or lower for some patients in Study JPBH, either the severity of diarrhea decreased or the event resolved.

The rationale for the underlying change in the abemaciclib starting dose is, that although the Phase 1 Study JPBA demonstrated that the 200 mg Q12H abemaciclib dose was tolerable when administered in combination with fulvestrant, a substantial number of patients required abemaciclib dose suspension and/or reduction during the first 2 treatment cycles. As a consequence of this observation, a review of dosing and tolerability data from patients enrolled during the first 5 months of this study was carried out as part of a regular blinded safety review to assess if a similar number of patients required dose alterations in the present study. During the review of blinded safety data from Study JPBL, any alteration in dosing of abemaciclib or placebo was presumed to have occurred on the abemaciclib arm. The data review did reveal a high number of dose alterations for abemaciclib or placebo. The cause of this was principally diarrhea occurring in the first treatment cycle. Therefore, the initial dose of blinded study drug administered in combination with fulvestrant will be reduced to 150 mg Q12H.

5.2. Rationale for Amendment (b)

Study JPBL protocol was amended to update the sample size for endocrine therapy pretreated (EP) patients enrolled at the 150-mg Q12H dose and to update the analysis plan. The EP population is defined as those patients with progression on adjuvant endocrine therapy or within 12 months of completion of adjuvant endocrine therapy, or those patients who have progressed on or after first-line endocrine therapy for metastatic disease. In addition, amendment (b) removes the inclusion of endocrine therapy naïve (EN) patients and specifies that the previously enrolled EN patients will not be included in the primary analysis.

Prior to amendment (b), this study enrolled 2 strata of patients according to prior endocrine therapy: EP patients and EN patients. Following the dose change in amendment (a), the study has been modified to focus the study objectives on the EP strata. Amendment (b) removes inclusion of EN patients. The intent-to-treat (ITT) population is limited to those patients identified as EP at study entry. Importantly, prior to amendment (b), randomization was stratified by sensitivity to prior endocrine therapy: no prior therapy (EN) versus primary resistance (EP) versus secondary resistance (EP). The narrowing of the ITT population excludes only those patients previously

randomized within a specific randomization stratum. As a result, the treatment balance is preserved within the revised ITT population and also remains balanced with respect to the other stratification factor (nature of disease).

The initial study protocol specified an enrollment of 450 EP patients. Amendment (a) changed the starting dose of blinded study drug from 200 mg Q12H to 150 mg Q12H. In addition to describing the safety profile in the full EP safety population, safety analyses will be conducted in the subgroup of patients enrolled under amendment (a) with a starting dose of 150 mg Q12H. In order to do this robustly, enrollment to the study will continue until 450 EP patients are enrolled at a starting dose of 150 mg Q12H. Including the approximately 180 EP patients enrolled at a starting dose of 200 mg Q12H prior to amendment (a), approximately 630 EP patients will be enrolled.

Further Amendment (b) modifications included: 1) moving secondary objectives pertaining to skeletal-related events (SREs) and changes in Eastern Cooperative Oncology Group (ECOG) performance status (PS) to exploratory objectives due to the low anticipated event rates in this study; 2) clarifying the EP population to be enrolled (Inclusion Criterion [2]); 3) limiting the timing of initiation of bone-modifying agents by adding Exclusion Criterion [26]; and 4) clarifying administration of fulvestrant during blinded study drug dose suspensions.

Minor typographical and formatting edits were made throughout the document for clarity and consistency.

5.3. Rationale for Amendment (c)

Study JPBL protocol was amended to update the dosing guidance for cases of hematologic toxicity and diarrhea, and guidance on the use of blood cell growth factors. Lilly conducted a review across several clinical trials of abemaciclib in breast cancer and concluded that there were some inconsistencies. This amendment will harmonize the dosing guidance and clarify that blood cell growth factors are only to be used in a manner consistent with American Society of Clinical Oncology (ASCO) guidelines.

The following were also included in the amendment: 1) caution when coadministering with substrate drugs of cytochrome P450s (CYPs) with narrow therapeutic margin and 2) an additional window of up to 3 days prior to Day 1 of each cycle is allowed for flexibility in obtaining central laboratory and imaging results.

Furthermore, the statistical analysis plan (SAP) was updated. Specifically, the interim analysis boundaries, timing of interim analyses, and overall survival analysis plan were modified.

Minor typographical and formatting edits were made throughout the document for clarity and consistency.

5.4. Rationale for Amendment (d)

Recent Phase 3 study disclosures (Cristofanilli et al. 2016) indicate the combination of fulvestrant and an inhibitor of CDK4 and CDK6 may be highly efficacious. Consequently, an

earlier final analysis will be conducted, after 378 PFS events, rather than the initially planned 441 events, which still maintains the power at approximately 90% for the target hazard ratio of 0.70. A total of 378 PFS events at the final analysis corresponds to a censoring rate of approximately 40%, which is consistent with that of other trials conducted in a similar setting (for example, Di Leo et al. 2010; Baselga et al. 2012; Yardley et al. 2013; Cristofanilli et al. 2016). A final analysis at 378 events precludes the need for a second interim analysis at 353 events, thus JPBL Amendment (d) removes the second interim analysis, leaving a single interim analysis at 265 events.

Minor typographical and formatting edits were made throughout the document for clarity and consistency.

5.5. Rationale for Amendment (e)

Study JPBL protocol was amended to update the safety language regarding hepatic monitoring, assessment of renal function, and venous thromboembolic events (VTEs) for ongoing patients. Cystatin C was added to the central laboratory chemistry panel for more thorough assessment of renal function. Changes to the dose adjustment and delay section and [Table JPBL.9.2](#) were done to specify dose modifications in response to Grade 2 diarrhea and increased alanine aminotransferase laboratory values.

Minor typographical and formatting edits were made throughout the document for clarity and consistency.

5.6. Rationale for Amendment (f)

This amendment to Study JPBL protocol updates the safety language monitoring and guidance for interstitial lung disease (ILD)/pneumonitis. Changes to the dose adjustment and delay section and [Table JPBL.9.2](#) were done to specify dose modifications in response to ILD/pneumonitis events. These updates are in alignment with changes made in the development core safety information of the IB. Similarly, Section 9.6 (Concomitant Therapy) was updated to align with the current IB.

Changes to the Special Hepatic Safety Data Collection were done to ensure a comprehensive evaluation of patients with treatment-emergent abnormal liver tests and to align with current guidance from the Lilly Liver and Gastrointestinal Safety Advisory Committee.

Minor typographical and formatting edits were made throughout the document for clarity and consistency. The projected date for Last Patient Visit was updated in the Synopsis (Section 2).

5.7. Rationale for Amendment (g)

This amendment to the Study JPBL protocol updates the dose adjustment guidance related to nonhematologic toxicity, ALT/AST increased, and VTEs to ensure alignment with the current IB. Specifically, protocol updates were made to the dose adjustment section for Nonhematologic Toxicity (Section 9.4.1.1.4) and its subsections, as well as corresponding updates in [Table JPBL.9.2](#). Additionally, the Concomitant Therapy (Section 9.6) information was updated for CYP3A modulators and transporter substrates. Finally, safety monitoring language in Section

10.3.3.3 for VTE was updated to align with the current IB, and Section 10.3.3.4 was edited for clarity to include specific ILD/pneumonitis Grades requiring abemaciclib discontinuation.

Minor typographical and formatting edits were made throughout the document for clarity and consistency.

6. Objectives

6.1. Primary Objective

The primary objective of Study JPBL is to compare abemaciclib plus fulvestrant versus placebo plus fulvestrant with respect to PFS for women with HR+, HER2- locally advanced or metastatic breast cancer.

6.2. Secondary Objectives

The secondary objectives of the study are to compare abemaciclib plus fulvestrant versus placebo plus fulvestrant with respect to each of the following:

- overall survival (OS)
- OS rate at 1, 2, and 3 years
- objective response rate [complete response (CR) + partial response (PR)]
- duration of response (DoR) [CR + PR]
- disease control rate (DCR) [CR + PR + stable disease (SD)]
- clinical benefit rate (CBR) [CR + PR + SD \geq 6 months]
- safety and tolerability
- pain and symptom burden using the Brief Pain Inventory (BPI), the European Organization for Research and Treatment of Cancer Quality of Life Questionnaire-Core 30 (EORTC QLQ-C30) and the EORTC QLQ-BR23 (breast) questionnaires, and health status scores from the EuroQol 5-Dimension 5 Level (EQ-5D 5L)
- pharmacokinetics (PK) of abemaciclib, its metabolites, and fulvestrant

6.3. Exploratory Objectives

- To explore potential biomarkers related to the retinoblastoma (Rb) pathway and/or the pathogenesis of breast cancer
- To explore if change in tumor size is associated with PFS and OS
- To explore time to progressive bone metastases by treatment arm
- To evaluate time to worsening of ECOG PS of \geq 2
- To evaluate time to first SRE (defined as either pathological fracture, spinal cord compression, radiation to the bone, or surgery to the bone)

7. Study Population

Individuals who do not meet the criteria for participation in this study (screen failure) may not be re-screened.

Study participants should be instructed not to donate blood or blood products during the study or for 9 months following the last dose of fulvestrant or 2 weeks following the last dose of blinded study drug, whichever is longer.

Prospective approval of protocol deviations to recruitment and enrollment criteria (also known as protocol waivers or exemptions) is not permitted.

7.1. Inclusion Criteria

Patients are eligible to be included in the study only if they meet **all** of the following criteria:

- [1] have a diagnosis of HR+, HER2- breast cancer
 - to fulfill the requirement of HR+ disease, a breast cancer must express, by immunohistochemistry (IHC), at least 1 of the hormone receptors (estrogen receptor [ER] or progesterone receptor [PgR]) as defined in the relevant American Society of Clinical Oncology (ASCO) / College of American Pathologists (CAP) Guidelines (Hammond et al. 2010).
 - to fulfill the requirement of HER2- disease, a breast cancer must not demonstrate, at initial diagnosis or upon subsequent biopsy, overexpression of HER2 by either IHC or in-situ hybridization as defined in the relevant ASCO / CAP Guidelines (Wolff et al. 2013). Although not required as a protocol procedure, a patient with a new metastatic lesion should be considered for biopsy whenever possible to reassess HER2 status prior to study entry if clinically indicated.
- [2] have locally advanced disease not amenable to curative treatment by surgery or metastatic disease. In addition, patients must fulfill 1 of the following criteria:
 - relapsed with radiologic evidence of progression while receiving neoadjuvant or adjuvant endocrine therapy, with no subsequent endocrine therapy received following progression
 - relapsed with radiologic evidence of progression within 1 year from completion of adjuvant endocrine therapy, with no subsequent endocrine therapy received following progression
 - relapsed with radiologic evidence of progression more than 1 year from completion of adjuvant endocrine therapy and then subsequently relapsed with radiologic evidence of progression after receiving treatment with either an antiestrogen or an aromatase inhibitor as first-line endocrine therapy for metastatic disease. Patients may not have received more than 1 line of endocrine therapy or any prior chemotherapy for metastatic disease.
 - presented de novo with metastatic disease and then relapsed with radiologic evidence of progression after receiving treatment with either an antiestrogen or an

aromatase inhibitor as first-line endocrine therapy for metastatic disease. Patients may not have received more than 1 line of endocrine therapy or any prior chemotherapy for metastatic disease.

- [3] have postmenopausal status due to either surgical/natural menopause or ovarian suppression (initiated at least 28 days prior to Day 1 of Cycle 1) with a gonadotropin-releasing hormone (GnRH) agonist such as goserelin. Postmenopausal status due to surgical/natural menopause requires at least 1 of the following:
- prior bilateral oophorectomy
 - age ≥ 60 years
 - age < 60 years and amenorrheic for at least 12 months (in the absence of chemotherapy, tamoxifen, toremifene, or ovarian suppression) and follicle-stimulating hormone (FSH) and estradiol levels in the postmenopausal range
- [4] have a negative serum pregnancy test at baseline (within 14 days prior to randomization) and agree to use medically approved precautions to prevent pregnancy during the study and for 12 weeks following the last dose of abemaciclib if postmenopausal status is due to ovarian suppression with a GnRH agonist
- [5] have either measurable disease or nonmeasurable bone only disease. Measurable and nonmeasurable disease are defined according to the Response Evaluation Criteria in Solid Tumors (RECIST Version 1.1 [v1.1], Eisenhauer et al. 2009; refer to [Attachment 5](#)). Nonmeasurable bone only disease may include any of the following: blastic bone lesions, lytic bone lesions without a measurable soft tissue component, or mixed lytic-blastic bone lesions without a measurable soft tissue component.
- [6] are female and ≥ 18 years of age
- [7] have given written informed consent prior to any study-specific procedures
- [8] have adequate organ function, including:
- hematologic: absolute neutrophil count $\geq 1.5 \times 10^9/L$, platelets $\geq 100 \times 10^9/L$, and hemoglobin ≥ 8 g/dL. Patients may receive erythrocyte transfusions to achieve this hemoglobin level at the discretion of the investigator; however, initial study drug treatment must not begin earlier than the day after the erythrocyte transfusion.
 - hepatic: bilirubin ≤ 1.5 times upper limit of normal (ULN) and alanine aminotransferase (ALT) ≤ 3.0 times ULN
 - renal: serum creatinine ≤ 1.5 times ULN
- [9] have a performance status ≤ 1 on the ECOG scale

- [10] have discontinued previous therapies for cancer (including specifically, aromatase inhibitors, anti-estrogens, chemotherapy, radiotherapy, and immunotherapy) for at least 21 days for myelosuppressive agents or 14 days for nonmyelosuppressive agents prior to receiving study drug, and recovered from the acute effects of therapy (until the toxicity resolves to either baseline or at least Grade 1) except for residual alopecia or peripheral neuropathy
- [11] are willing to participate for the duration of the study and to follow study procedures
- [12] are able to swallow capsules

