Diagnosis and Main Criteria for Inclusion and Exclusions: Patients are eligible to be included in the study if they meet following criteria: 1) have a diagnosis of HR+, HER2- breast cancer; 2) have inoperable locally advanced or metastatic disease and relapsed with radiologic evidence of progression; 3) have postmenopausal status due to either surgical/natural menopause or ovarian suppression with a gonadotropin-releasing hormone (GnRH) agonist such as goserelin; 4) have a negative serum pregnancy test at baseline (within 14 days prior to randomization) and agree to use medically approved precautions to prevent pregnancy during the study and for 12 weeks following the last dose of abemaciclib if postmenopausal status is due to ovarian suppression with a GnRH agonist; 5) have either measurable disease or nonmeasurable bone only disease; 6) are female and ≥ 18 years of age; 7) have given written informed consent prior to any study-specific procedures; 8) have adequate organ function; 9) have a performance status ≤ 1 on the ECOG scale; 10) have discontinued previous therapies for cancer, for at least 21 days for myelosuppressive agents or 14 days for nonmyelosuppressive agents prior to receiving study drug, and recovered from the acute effects of therapy; 11) are willing to participate for the duration of the study and to follow study procedures; and 12) are able to swallow capsules.

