7.3. Discontinuations

7.3.1. *Discontinuation of Patients*

The criteria for enrollment must be followed explicitly. If the investigator site identifies a patient who did not meet enrollment criteria and who was inadvertently enrolled, the sponsor must be notified. If the sponsor identifies a patient who did not meet enrollment criteria and who was inadvertently enrolled, the investigator site will be notified. A discussion must occur between the sponsor CRP and the investigator to determine whether the patient may continue in the study, with or without study drug. Inadvertently enrolled patients may be maintained in the study and on study drug when the Lilly CRP agrees with the investigator that it is medically appropriate for that patient. The patient may not continue in the study with or without study drug if the Lilly CRP does not agree with the investigator's determination that it is medically appropriate for the patient to continue. The investigator must obtain documented approval from the Lilly CRP to allow the inadvertently enrolled patient to continue in the study with or without study drug.

In addition, patients will be discontinued from the study drug(s) and/or from the study in the following circumstances:

- Progressive disease (PD) as defined by RECIST v1.1.
- enrollment in any other clinical trial involving an investigational product or enrollment in any other type of medical research judged not to be scientifically or medically compatible with this study
- investigator decision
 - the investigator decides that the patient should be discontinued from the study or study drugs
 - if the patient, for any reason, requires treatment with another therapeutic agent that has been demonstrated to be effective for treatment of the study indication, discontinuation from the study drugs occurs prior to introduction of the new agent
- patient decision
 - the patient or the patient's designee (for example, parents or legal guardian) requests to be withdrawn from the study or study drug
- sponsor decision

- Lilly stops the study or stops the patient's participation in the study for medical, safety, regulatory, or other reasons consistent with applicable laws, regulations, and good clinical practice (GCP)

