- **Baseline:** begins when the informed consent form (ICF) is signed and ends at the first study treatment (or at discontinuation, if no treatment is given).
- **Study Period:** begins at the first study treatment and ends at study completion. The study period does not include the extension period.
 - **Study Treatment Period:** begins at the first study treatment and ends when the patient and the investigator agree that the patient will no longer continue study treatment. The date of this agreement is to be reported on the electronic case report form (eCRF) as the Date of Discontinuation from study treatment.
 - **Postdiscontinuation Follow-Up:** begins the day after the patient and the investigator agree that the patient will no longer continue study treatment.

Short-term follow-up begins the day after the patient and the investigator agree that the patient will no longer continue study treatment and lasts approximately 30 days.

[figure not shown]
Long-term follow-up begins the day after short-term follow-up is completed and continues until the patient's death or overall study completion.

- **Extension Period:** begins after study completion and ends at the end of trial. During the extension period, patients on study therapy who continue to experience clinical benefit may continue to receive study therapy until one of the criteria for discontinuation is met. The extension period includes extension period short-term follow-up.
 - Extension period short-term follow-up: begins the day after the patient and the investigator agree that the patient will no longer continue study treatment in the extension period and lasts approximately 30 days.

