8.1.2. Extension Period

After study completion, all patients who are on study treatment and who are eligible for the extension period will be unblinded. Patients receiving study treatment and experiencing ongoing clinical benefit may continue to receive study treatment in the extension period until one of the criteria for discontinuation is met (Section 7.3). During the extension period, placebo will no longer be administered, and crossover will not be permitted. Lilly will notify investigators when the extension period begins.

Patients who are in short-term follow-up when the extension period begins will continue in short-term follow-up until the 30-day short-term follow-up visit is completed. Long-term follow-up does not apply.

Patients who are in long-term follow-up when the extension period begins will be discontinued from long-term follow-up.

During the extension period, all AEs, SAEs, and study drug exposure will be reported on the eCRF. Serious adverse events will also be reported to Lilly Global Patient Safety (GPS) (see Section 10.3.1). In the event that an SAE occurs, Lilly may request additional information (such as local laboratory results, concomitant medications, and hospitalizations) in order to evaluate the reported SAE.

Investigators will perform any other standard procedures and tests needed to treat and evaluate patients; however, the choice and timing of the tests will be at the investigator's discretion. Lilly will not routinely collect the results of these assessments.

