10.3. Safety Evaluations

Investigators are responsible for monitoring the safety of patients who have entered this study and for alerting Lilly or its designee to any event that seems unusual, even if this event may be considered an unanticipated benefit to the patient.

The investigator is responsible for the appropriate medical care of patients during the study.

The investigator remains responsible for following, through an appropriate health care option, AEs that are serious, considered related to the study, or that caused the patient to discontinue before completing the study. The patient should be followed until the event is resolved or explained. Frequency of follow-up evaluation is left to the discretion of the investigator.

The timing of all safety evaluations is shown in the Study Schedule ([Attachment 1](#)).

[Table JPBL.10.3](#) presents a summary of AE and SAE reporting guidelines. [Table JPBL.10.3](#) also shows which database or system is used to store AE and SAE data.

Table JPBL.10.3. Adverse Event and Serious Adverse Event Reporting Guidelines

Period	Types of AEs/SAEs to be Reported	Collection Database	Lilly Safety System
Baseline (pretreatment)	Preexisting conditions	x	
	All AEs	x	
	SAEs related to protocol procedures	x	x
Study treatment period	All AEs	x	
	All SAEs	x	x
30-day short-term postdiscontinuation follow-up	All AEs	x	
	All SAEs	x	x
Long-term postdiscontinuation follow-up	All SAEs related to protocol procedures or study drug or drug delivery system	x	x
Extension period	All AEs	x	
	All SAEs	x	x
Extension period follow-up	All AEs	x	
	All SAEs	x	x
After the patient is no longer participating in the study (that is, no longer receiving study therapy and no longer in follow-up)	All SAEs related to protocol procedures or study drug or drug delivery system that the investigator becomes aware of		x

Abbreviations: AEs = adverse events; SAEs = serious adverse events.

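### The only post-dose pregnancy-precaution window runs from abemaciclib; none runs from fulvestrant, which leaves a gap for a small group of GnRH-suppressed women

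*Protocol*

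**What the plan says.** Protocol Section 7.1, criterion [4], applies to women whose postmenopausal status is due to a GnRH agonist. Besides a negative pregnancy test, they must "agree to use medically approved precautions to prevent pregnancy during the study and for 12 weeks following the last dose of abemaciclib". Synopsis item 4 has the same rule: "precautions to prevent pregnancy during the study and for 12 weeks following the last dose of abemaciclib".

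The opening of Section 7 (Study Population) sets a blood-donation rule that names both drugs: "9 months following the last dose of fulvestrant or 2 weeks following the last dose of blinded study drug, whichever is longer".

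Other relevant text:

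- Section 9.1 gives fulvestrant to both arms and counts fulvestrant alone as study treatment. Section 9.4.1.1.1.1 lets it continue after blinded drug is discontinued.
- Section 7.3.1 allows for a patient who "requests to be withdrawn from the study or study drug".
- Section 8.1 states: "The study period does not include the extension period". Extension follow-up starts once patient and investigator agree that she will "no longer continue study treatment in the extension period and lasts approximately 30 days".
- Section 8.1.2 unblinds patients entering the extension and closes long-term follow-up. It adds: "During the extension period, placebo will no longer be administered, and crossover will not be permitted".
- Section 9.6.7 asks for the GnRH agonist to continue while study treatment lasts and says nothing about the time after it.

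**The concern.** Criterion [4] counts its post-treatment window from one of the two drugs. Fulvestrant can be the last drug taken in either arm, and for control-arm women in the extension it is the only one. The blood-donation rule shows that the sponsor recognised a long post-fulvestrant period and knew how to write a rule for two drugs. The contraception rule does not do the same.

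At stake is possible fetal exposure after treatment in women whose ovarian function is suppressed by a drug and not permanently lost. The continuing GnRH agonist lowers the risk during dosing. Nothing requires it afterwards, and that ovarian function then returns is an assumption.

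**Working it through.** **Reading used.** The phrase *during the study* is not defined in criterion [4]. I take the most protective reading available. Table JPBL.10.3 describes the time "After the patient is no longer participating in the study (that is, no longer receiving study therapy and no longer in follow-up"), so a woman counts as participating while she is on study therapy or in follow-up, including extension dosing. While the trial is blinded, I count the 12 weeks from the last blinded dose in both arms.

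**Cover after the last fulvestrant dose.** Let k be the weeks from the last oral dose to the last fulvestrant dose.

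| Situation | Calculation | Weeks of cover |
|---|---|---|
| Withdraws at or soon after last dose; both drugs end the same day | 12 | 12 |
| Same, but fulvestrant on Day 1 and oral drug to Day 28 | 27/7 + 12 | 15.9 |
| Withdraws at her last fulvestrant dose, after k weeks on fulvestrant alone | max(0, 12 − k) | 0 once k reaches 12 |
| In follow-up, last dose close to study completion | later of study completion, the 30-day visit and the 12-week clock | 12 to 15.9 at least, if the drugs ended within the same cycle |
| Extension, abemaciclib arm, on both drugs | as rows 1 and 2 | 12 to 15.9 |
| Extension, control arm, fulvestrant stops well after placebo | 30/7 if the decision to stop falls on the day of the last dose; (27 + 30)/7 if on Day 28 | 4.3 to 8.1 |

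The last row applies only once the 12 weeks from the last placebo dose have been overtaken. That is when 12 − k falls below 4.3 (k above 7.7 weeks) or below 8.1 (k above 3.9 weeks). If fulvestrant stops soon after placebo, cover is longer, and about 12 weeks if both stop together.

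A woman who stays in follow-up keeps her cover to study completion, however long ago she stopped treatment.

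**How many women.** Inputs from Protocol Section 12.1: 630 patients randomized 2:1 (420 and 210), control median PFS 6.5 months, hazard ratio 0.703, exponential times, final OS analysis at 441 deaths. The planned figure reproduces: 6.5/0.703 = 9.25 months, a gain of 2.75 months (42%). PFS stands in for time on fulvestrant.

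- Rates per month: control ln 2/6.5 = 0.1066; abemaciclib ln 2/9.25 = 0.0750.
- With uniform accrual over A months and completion at month T, the expected fraction progression-free is [exp(−λ(T − A)) − exp(−λT)]/(λA). A = 24 months is assumed.
- *Completion at 441 deaths.* 441/630 = 70% dead. The Introduction puts median OS for metastatic breast cancer at 2 to 3 years. With an exponential median of 24 months, T is 54.4 months and 20.0 + 3.0 = about 23 patients are progression-free. With 36 months, T is 75.0 and 4.3 + 0.3 = 4.6 are (4.1 with no accrual spread).
- *Completion at the planned study length of about 112 months (Synopsis).* 0.266 + 0.006 = about 0.3 patients. This is a low end, because 112 months runs to the planned last visit and study completion may come earlier.

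The range is therefore about 0.3 to 23 of 630, of whom 0.006 to 3.0 are in the control arm. Nine months before completion, the same model gives about 0.5 to 47 progression-free, an upper guide to those whose last dose could fall close to completion. All counts are before restriction to GnRH-suppressed women, whose share the documents do not give, and leave out withdrawals.

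**The case against.** The strongest reply is that the study clause does most of the work. Long-term follow-up runs to death or study completion, so a woman who stops treatment and stays in follow-up is covered well past 12 weeks. That stands. A reader might infer that all GnRH-suppressed women lose cover 12 weeks after abemaciclib; the text does not say so.

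A reader might also infer that 9 months is the required contraception interval, and read 9 × 30.44/7 = 39.1 weeks minus 12 as a 27-week breach. The documents do not support that. The 9 months is a blood-donation interval with a different purpose. It shows that the protocol recognises a long post-fulvestrant period, but it cannot show that 12 to 16 weeks is too short.

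A third tempting inference is that precautions lapse during extension dosing, because Section 8.1 excludes the extension from the study period. That needs *during the study* to mean the defined study period, and criterion [4] does not use that term. The point here does not rely on it.

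Finally, the Introduction refers fulvestrant's risks to its label, and the consent pages were removed before review. Either may state an interval, so it is not established that patients lack an instruction. GnRH suppression during treatment also lowers the risk. These replies reduce the weight of the point. None supplies a protocol window that starts from fulvestrant.

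**Conclusion.** The point holds as a limited gap in the protocol text. No visible provision sets pregnancy precautions from the last fulvestrant dose. On the most protective reading, the gap is confined to women who withdraw, women whose last fulvestrant dose is close to study completion, and women treated in the extension. Control-arm women in the extension are the clearest case, since criterion [4] gives them no abemaciclib dose to count from.

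The size is small and uncertain. It rests on exponential PFS and OS, an assumed 24-month accrual, a general survival range for metastatic disease, and a completion date that the sponsor decides. No endpoint, sample size or analysis is affected. This is a worthwhile patient-safety improvement at low cost, not evidence that harm has occurred or that patients are uninformed.

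**What to change.** Require precautions throughout all study treatment, including the extension, and until the later of:

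1. 12 weeks after the last dose of blinded study drug or abemaciclib; and
2. an interval after the last dose of fulvestrant, set by the sponsor and matched to the fulvestrant label or consent form. The 9-month blood-donation interval serves as a reference point only.

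Put the rule in criterion [4] and Synopsis item 4. An entry criterion alone does not reach women already enrolled, so also put it in Sections 8.1.2 and 9.6.7 and in the patient instructions. No contact is scheduled after the 30-day extension follow-up visit, so the instruction must be given by then.

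The cost is amendment and consent wording, and longer precautions for a small subgroup. Amendment (e) already changed safety text for ongoing patients, so the route exists.
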